In order to be a Drill Sergeant Instructor, the Soldier must have achieved a rank of E5 (Sergeant) or higher, which generally takes between 4 to 5 years to obtain. Soldiers in DSS training are generally male (87%), between 21 – 45 years of age and racially diverse. In addition, Soldiers are routinely excluded from participation in DSS training if they have any driving under the influence convictions; domestic violence accusations or if they are under any Uniform Code of Military Justice (UCMJ) action or have any felony convictions. Soldiers are routinely screened for drug use by urinalysis and are excluded if test results are positive. They are also excluded if they fail to pass the Physical Training (PT) test, are restricted from any PT activity, or fail to meet weight, height or pregnancy restrictions.

4.4 Inclusion Criteria:

1. Male or female
2. 21 to 45 years of age
3. Negative pregnancy test confirmed by urine sample at enrollment and prior to taking first study drug dose.
4. Willing to use an effective method of birth control during the study (Female participants should avoid pregnancy and male participants should avoid fathering children during study). *Subject should either abstain from sexual relations or practice a method of birth control while taking part in the study. Except for surgical removal of the uterus, birth control methods such as condoms, a diaphragm or cervical cap, birth control pills, IUD, or sperm killing products are not totally effective in preventing pregnancy. Male study participants should refrain from fathering babies while enrolled in this study.*
5. Pure tone air conduction threshold average at 0.5, 1 and 2 kHz of no greater than 40 dB HL bilaterally with no air bone gaps greater than 10 dB and normal otoscopy and tympanometry screens.
6. Willing to limit the use of nutritional supplements containing or derived from protein to 50 grams of protein per day while participating in this study.
7. Ability to comply with all study requirements

4.5 Exclusion Criteria:

Most of these exclusion criteria apply to DSS candidates, but also apply in this study:

1. History of allergic or idiosyncratic reaction to methionine, amino acid mixtures, nutritional supplements, egg white or other proteins or food additives
2. Vegetarian (Individual excludes meat and fish from their diet)
3. History of chronic balance disorders

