5.5.3 Pure Tone Air Conduction Threshold/Bone Conduction Testing

Pure-tone air conduction threshold testing both at baseline and post-treatment (11-15 days after the last day of study drug/placebo administration) will be conducted utilizing the modified Hughson-Westlake procedure. Pure-tone air-conduction testing will be conducted at .5, 1, 2, 3, 4, 6, 8 kHz. Bone conduction testing will be conducted at .5, 1, 2, 3, 4 kHz if the pure tone air-conduction threshold at that frequency is greater than or equal to 15 dB HL. All testing will be conducted using standard Army test procedures using Interacoustic 629 clinical audiometers meeting all Defense Occupational Environmental Health

Readiness System – Hearing Conservation (DOEHRS-HC) and American National Standards Institute (ANSI) criteria. All testing will be conducted in a single -walled sound booth with doors closed, meeting ANSI specifications. Test equipment, test environment, procedures, and personnel will meet all relevant DOEHRs-HC, ASHA, AAA, and ANSI standards and guidelines.

Pure-tone threshold testing will be conducted using the modified Hughson Westlake procedure as follows: Initial descent towards threshold is accomplished in 10-dB steps. Beginning with the first non-response, level is increased by 5-dB for each non-response, and decreased by 10-dB after each correct detection response. Threshold is defined as the lowest level at which two responses are obtained out of three presentations on an ascending run.

Threshold shifts will also be evaluated using DoD significant change criteria and ASHA early detection criteria (1994). Significant noise-induced threshold shifts (STS) in either ear are defined by the DOEHRs-HC as an increase of 10 dB or greater change (decrease in hearing) for the average of 2, 3 AND 4 kHz in either ear. A significant negative STS (improved hearing) is defined as a decrease of 10 dB or greater change (improvement in hearing) for the average of 2, 3 AND 4 kHz in either ear. An early warning shift STS (decrease in hearing) is defined as a 15 dB or greater change at 1, 2, 3 OR 4 kHz in either ear. Subjects with an STS will undergo a final tympanogram screen to rule out middle ear pathology as a cause of the hearing loss. If they pass the tympanogram screen in both ears, they will be referred for a diagnostic audiologic follow-up exam. If they do not pass the tympanogram screen they will be referred for otologic check and then diagnostic audiological assessment.

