10.0 STATISTICAL CONSIDERATIONS

10.1 Sample Size Justification

Based upon the results of the 2004 study at the Marine Corps Recruit Depot (MCRD), it is estimated that the rate of significant threshold shift (STS) will be approximately 38% for the control (placebo) group. A power analysis incorporating a 95% confidence level ($\alpha = 0.05$), 80% power, a 1:1 ratio (placebo to D-methionine), and a detectable difference in threshold shift rates of 30% yields a required sample size of 252 subjects for each of the two arms (placebo and D-methionine) of the study. Thus a total of 504 subjects need to complete the study. Assuming an attrition rate of 20% in each arm over the course of the study, a total of 600 subjects will need to be enrolled.

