10.2 Primary Efficacy Analysis

Two groups are planned in the randomized prospective design: the D-met and the placebo groups. The primary objectives, and their associated analyses, for this study are as follows:

1. To determine if there is a significant difference between the D-methionine and placebo treated groups in the average severity of documented side effects where severity is defined as the frequency of side effect multiplied by the intensity of the side effect. Repeated measures analysis of variance (ANOVA) will be utilized to determine significance.
2. To determine if there is a significantly reduced change in threshold hearing in each ear, adjusting for handedness, for the D-methionine group as compared to the placebo group at the tested audiometric frequencies. The tested audiometric frequencies will be 0.5, 1, 2, 3, 4, 6 and 8 kHz. Multi-way (2 groups x 7 frequencies) analysis of variance (ANOVA) with interaction effects and correction for multiple comparisons (Newman-Keuls) will be utilized to determine significance. Determination for early detection will be according to the American Speech-Language Hearing Association (ASHA, 1994) criteria of: 1) greater than or equal to a 20 dB change at any frequency, 2) greater than or equal to a 10 dB change at any 2 adjacent frequencies, or 3) loss of response at 3 consecutive frequencies where responses were obtained at baseline. To be considered significant ototoxicity, these changes must replicate within 24 hours (may be immediate) with no indication of middle ear abnormality. Subjects serve as their own controls for audiometric change, which is computed relative to baseline measures.
3. To determine if there is a significantly lower rate of STS (in either ear) for the D-methionine group as compared to the placebo group where STS is defined according to DOEHRSHC criteria as an increase of 10 dB or greater change (decrease in hearing) for the average of 2, 3 AND 4 kHz in

either ear. A significant negative STS (improved hearing) is defined as a decrease of 10 dB or greater change for the average of 2, 3 AND 4 kHz in either ear. An early warning shift STS (decrease in hearing) is defined as a 15 dB or greater change at 1, 2, 3 OR 4 kHz in either ear. Fisher's exact test will be utilized to determine statistical significance.

Secondary objective of the study is as follows:

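### The primary STS test is valid but inefficient: Fisher's exact test costs about 3 points of power, and adjusting for baseline 2-3-4 kHz hearing may recover a little more

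*Combined protocol and SAP*

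**What the plan says.** Section 10.1 sizes the trial on STS alone. For placebo, "it is estimated that the rate of significant threshold shift (STS) will be approximately 38% for the control (placebo) group", and "a detectable difference in threshold shift rates of 30% yields a required sample size of 252 subjects" per arm at 80% power and alpha 0.05. Objective 3 in section 10.2 is "To determine if there is a significantly lower rate of STS (in either ear) for the D-methionine group" compared with placebo. STS there means a worsening of at least 10 dB in the 2, 3 and 4 kHz average in either ear. For the test, "Fisher's exact test will be utilized to determine statistical significance". No covariate is named. The only adjustment in section 10.2 is for handedness, in the separate threshold-change ANOVA. Section 5.4 describes 1:1 randomisation and mentions no stratification by baseline hearing.

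The baseline data exist. Section 5.5.3 provides for "Pure-tone air conduction threshold testing both at baseline and post-treatment" at seven frequencies that include 2, 3 and 4 kHz. Audiometry is also needed for eligibility. The entry criterion in section 4.4 is "Pure tone air conduction threshold average at 0.5, 1 and 2 kHz of no greater than 40 dB HL bilaterally", which sets no upper limit at 3 or 4 kHz.

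**The concern.** Two separate features cost power in the comparison that carries the stated 80%.

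First, Fisher's exact test is conservative: at these rates and sample sizes its true type I error is below the nominal 5%, and power falls with it.

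Second, baseline hearing enters only through the subtraction that defines STS. If the risk of a 10 dB shift still depends on where a subject starts, that dependence stays in the error term. Such dependence is possible. Section 2.1 places the noise notch near 4 kHz, section 4.3 says candidates generally have 4 to 5 years of service, and 3 and 4 kHz are uncapped at entry, so baseline high-frequency hearing may vary.

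At stake is a few points of power, not the validity of the result.

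**Working it through.** **Inputs.** From section 10.1: placebo rate 0.38, a 30% difference, alpha 0.05, power 80%, 252 completers per arm. Reading 30% as relative gives 0.38 × 0.70 = 0.266 on active. Read as absolute (38% v 8%) it would need only 30 per arm, so that reading cannot be the source of 252. Sidedness is not stated; two-sided is assumed.

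**1. The plan's own figure.** With pooled rate (0.38 + 0.266)/2 = 0.323 and difference 0.114:

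n = [1.96·√(2·0.323·0.677) + 0.8416·√(0.38·0.62 + 0.266·0.734)]² / 0.114² = (1.2962 + 0.5524)² / 0.012996 ≈ 263 per arm, or 281 with continuity correction.

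The stated 252 is not reproduced. It is nearly matched if the active rate is taken as 26%, with continuity correction (253).

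**2. Unadjusted power at 252 per arm, 38% v 26.6%.**

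- Normal approximation: Φ[(0.114·√252 − 1.2962)/0.6564] = Φ(0.782) = 78.3%.
- Pearson test, by exact enumeration of both binomials: 78.5%, actual size 4.9%.
- Fisher's exact test, same enumeration: 75.6%, actual size about 4.0%.

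Fisher's conservatism therefore costs 78.5 − 75.6, about 3 points, with no covariate involved. Fisher would need about 280 per arm for 80%. If 20% of 600 are lost, 240 per arm remain, and power is 73.4% for Fisher and 76.4% for Pearson.

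**3. Further gain from a baseline covariate.** The documents give no correlation rho between baseline hearing and STS, so rho is an assumption. Using effective n = 252/(1 − rho²) in the formula of step 2:

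| rho | rho² | effective n per arm | power | gain over rho = 0 |
|---|---|---|---|---|
| 0 | 0 | 252 | 78.3% | 0 |
| 0.2 | 0.04 | 262.5 | 79.9% | 1.6 |
| 0.3 | 0.09 | 276.9 | 82.0% | 3.7 |
| 0.35 | 0.1225 | 287.2 | 83.4% | 5.1 |
| 0.5 | 0.25 | 336 | 88.7% | 10.4 |

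**4. Check by simulation** (4,000 trials per setting, same marginal rates). R² is the share of STS variance explained by baseline. Baseline-adjusted logistic regression had power of 78.4% at R² = 0, 80.5% at 0.05, 82.0% at 0.11 and 84.8% at 0.17. Its size stayed between 4.6% and 5.2%. Unadjusted logistic regression stayed at 77.9% to 78.6% in those settings. An uninformative covariate carried no penalty.

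**5. Which rho is plausible?** A second simulation, resting wholly on assumed values, took either-ear STS with true baseline SD 6 or 10 dB, measurement error SD 2 or 4 dB and shift SD 4 or 8 dB. With baseline and shift linked only by measurement error, R² was 0.001 to 0.034, that is, rho about 0.03 to 0.18 and a gain of at most about 1.5 points. Larger values needed the true shift itself to depend on baseline hearing. With an assumed dependence of 0.3 dB per dB, in either direction, R² ran from 0.001 to 0.194.

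**The case against.** The strongest reply is that nothing is wrong. Fisher's test controls type I error, the sample size does not rely on adjustment, and no section says that baseline 2-4 kHz hearing predicts STS. STS is already baseline-referenced, so much of the usual gain from adjustment has been taken. Poorer baseline hearing could mean less room to shift or greater susceptibility, and if both operate a linear term gains little. All of this stands, and it is why the point is one of efficiency only.

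A second reply is that 252 may already allow for Fisher's conservatism. Taking the active rate as 26%, the continuity-corrected formula gives 253, and exact enumeration as in step 2 gives Fisher 80.2% power at 252. That stands as a possible reading, but section 10.1 does not state 26%, and 30% of 38% gives 26.6%. Even at 26% the Pearson test is more powerful, at 82.7%.

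A reader might infer more than the documents support, in three ways:

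- *That ignoring baseline forfeits 10 points or so of power.* This needs rho near 0.5. With STS in about 32% of subjects and a normally distributed covariate, baseline alone would have to discriminate STS with an AUC of about 0.81. Even rho 0.35 needs about 0.71. The documents support neither.
- *That the whole shortfall comes from omitting baseline.* About 3 points come from Fisher's test itself and could be recovered without a covariate.
- *That chance imbalance would bias the STS result.* The type I error already covers it. With 252 per arm, the standard error of the baseline difference is √(2/252), about 0.09 SD.

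Finally, this is a change to the primary test of a recruiting trial, so it is more than a wording edit. That also stands and is counted under the cost.

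**Conclusion.** The planned STS test is valid but inefficient. On the relative reading of the 30% difference, two-sided 0.05 and 252 per arm, it has 75.6% power against about 78% for an unadjusted Pearson or likelihood-ratio test. That loss of about 3 points follows from the plan's own figures.

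The gain from adding baseline is conditional on a correlation that the documents do not give. It is under 2 points at rho 0.2 or less, the range expected if measurement error is the only link; about 4 points at 0.3; and 5 at 0.35. Rho 0.5 is an upper scenario without support in the documents.

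The point concerns only the binary STS comparison, not the threshold-change ANOVA. The differences between 263 and 252, and between 504/0.80 = 630 and the 600 to be enrolled, are separate sizing matters and do not strengthen it. It is an optional improvement, not a correction of an error.

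**What to change.** Amend section 10.2, objective 3, so that:

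- The primary STS test is the likelihood-ratio test of treatment in a logistic regression of STS on treatment and one named covariate: the mean of the right- and left-ear baseline 2-3-4 kHz averages.
- The headline estimate is the covariate-standardised difference in STS rates with its 95% CI, in keeping with the intervals that section 10.2 promises for all treatment differences.
- Fisher's exact test is kept as a sensitivity analysis.

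The amendment should be dated before any efficacy comparison by arm and written by staff blinded to allocation. Section 8.8 leaves the Yale statistician on the monitoring committee unblinded, and the roles section gives the statistical analyses to Yale, so the authorship should be documented.

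No new data are needed. The cost is a protocol amendment to a primary test in a recruiting trial, with the scrutiny that brings, and HRPO pre-approval under section 8.10 if it is classed as major. The model tests a conditional odds ratio, so its p-value may occasionally disagree with the risk-difference interval. The amendment should say in advance which governs.

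### 600 enrolled less 20% attrition leaves 240 per arm, not 252, and at 240 the named Fisher's exact test has about 73% to 78% power, not the stated 80%

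*Combined protocol and SAP*

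**What the plan says.** Section 10.1 (Sample Size Justification) puts the STS rate at "approximately 38% for the control (placebo) group". "A power analysis incorporating a 95% confidence level", 80% power, 1:1 allocation and "a detectable difference in threshold shift rates of 30" percent "yields a required sample size of 252 subjects for each of the two arms". It continues: "Thus a total of 504 subjects need to complete the study". It then assumes 20% attrition in each arm and sets enrolment at 600.

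Section 10.1 gives no treatment-arm rate. It does not say whether the 30% is relative or absolute, whether the test is one- or two-sided, or which test or formula produced 252.

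In section 10.2 (Primary Efficacy Analysis), the third primary objective begins "To determine if there is a significantly lower rate of STS (in either ear" and says that Fisher's "exact test will be utilized to determine statistical significance". Section 10.3 allows the final sample size to move up or down after an interim look at the placebo shift rate.

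**The concern.** Two things do not fit together. First, the number enrolled, the attrition rate and the number of completers in section 10.1 are mutually inconsistent. The trial's own attrition assumption takes it below the sample size on which its power statement rests. Second, the power is stated without a treatment rate or a test, while the analysis section names a test that is conservative at these sample sizes. A reader cannot tell whether 80% applies to that test.

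The stake is the chance of missing a real effect on the one primary comparison for which the trial was sized. A type II error rate of 22% to 27%, where 20% is stated, matters in a trial that is meant to support an efficacy claim. The interim re-sizing starts from the same calculation, so the gaps in 10.1 carry into that decision.

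**Working it through.** **Inputs.** From 10.1: placebo rate 0.38, a 30% difference, α = 0.05, power 80%, 1:1 allocation, 252 per arm, 504 completers, 20% attrition, 600 enrolled. From 10.2: Fisher's exact test. Assumed, because not stated: two-sided testing, and a treatment rate of either 0.38 × 0.70 = 0.266 (relative reduction) or 0.26 (inferred below).

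**Step 1. Can 252 be reproduced?** The usual formula is

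n = [z₀.₉₇₅ √(2p̄(1−p̄)) + z₀.₈₀ √(p₁(1−p₁) + p₂(1−p₂))]² / (p₁−p₂)²

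- 0.38 vs 0.266: p̄ = 0.323, n = (1.960 × 0.6613 + 0.842 × 0.6564)² / 0.114² = 262.9, so 263. With continuity correction, 281.
- 0.38 vs 0.26: p̄ = 0.32, n = (1.960 × 0.6597 + 0.842 × 0.6542)² / 0.12² = 236.0. With continuity correction, (236.0/4) × [1 + √(1 + 4/(236.0 × 0.12))]² = 252.4.
- One-sided, 0.38 vs 0.266: 208, or 225 corrected.
- Absolute 30 points, 0.38 vs 0.08: 30, or 37 corrected.

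Of the readings tried, 38% vs 26% with a continuity correction matches 252. Fisher's test at those rates matches too: its exact power is 79.98% at 251 per arm and 80.16% at 252. The 26% appears nowhere in the documents.

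**Step 2. Attrition.**

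- 600 × (1 − 0.20) = 480, or 240 per arm.
- Enrolment needed for 504 completers: 504 / 0.80 = 630.
- Loss that 600 can absorb: 1 − 504/600 = 16%.

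**Step 3. Exact power.** Power is the sum of the two binomial probabilities over every 2×2 outcome that the test rejects. Fisher's two-sided p-value uses the minimum-likelihood rule. Boschloo's test takes Fisher's p-value as its statistic, with the critical value set so that the maximum size over a grid of common rates is at most 5%.

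| Treatment rate | n per arm | Normal approximation | Fisher | Boschloo |
|---|---|---|---|---|
| 26.6% | 252 | 78.3% | 75.6% | 77.8% |
| 26.6% | 240 | 76.3% | 73.4% | 75.9% |
| 26% | 252 | 82.5% | 80.2% | 82.1% |
| 26% | 240 | 80.7% | 78.1% | 80.3% |

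Fisher's actual size is about 3.8% to 4.1% for common rates of 20% to 38%. Boschloo's maximum size on the grid is 4.97%.

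**Step 4. What causes the gap.** At 252 per arm and 26.6%, the shortfall is 80 − 75.6 = 4.4 points. The normal approximation is already 80 − 78.3 = 1.7 points short, so Fisher's conservatism accounts for 78.3 − 75.6 = 2.7 points. Falling from 252 to 240 per arm costs a further 2.2 points (75.6 to 73.4). At 26%, there is no shortfall at 252, and the loss at 240 is 80.2 − 78.1 = 2.1 points, all from attrition.

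**Step 5. Size needed.** At 26.6%, Fisher first reaches 80% at 279 per arm, or 279 / 0.80 = 348.75, so 349 enrolled per arm (698 in total). At 26%, it needs 252 per arm, or 630 enrolled.

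**The case against.** The strongest reply is that the trial may have been sized for Fisher's test. At 38% vs 26%, both the continuity-corrected formula and Fisher's own exact power give 252, and no other reading tried does. A reader might infer from the 75.6% figure that the sample size calculation ignored Fisher's conservatism, or that the named test cannot deliver 80% at 252. The documents do not support either inference. They do not name the method behind 252, and the 26.6% needed to show a shortfall there does not itself reproduce 252.

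A second reply is that the third objective is worded directionally. One-sided Fisher at 0.05 with 26.6% gives 84.1% at 252 and 82.8% at 240, so a one-sided plan would meet 80% even after attrition. That cannot be excluded on the text. However, no one-sided test is declared, the one-sided formula gives 208 or 225 rather than 252, and 10.2 calls for 95% confidence intervals on all group differences, which fits two-sided testing better. An absolute difference of 30 points would give almost 100% power, but it would need only 30 to 37 per arm.

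Third, Fisher's test is valid and standard, and it serves only one of three primary objectives. Naming it is not an error. Boschloo's test does not close the gap at 26.6% either.

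Fourth, section 10.3 makes the final sample size provisional. That is so, but the re-sizing responds only to the placebo rate. It corrects neither the attrition arithmetic nor the missing inputs, and it could reduce the sample.

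The first and third replies limit the point at 252 per arm. None of the four repairs the mismatch between 600, 20% and 504.

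**Conclusion.** The point holds for the sample that the plan itself expects to have. With 20% attrition, 600 enrolled leaves 240 per arm, 12 fewer than the 252 on which the stated power rests. This part is plain arithmetic and needs no assumption. At 240 per arm, two-sided Fisher at 0.05 falls short of 80% at both candidate treatment rates, by 6.6 points at 26.6% (73.4%) and by 1.9 points at 26% (78.1%).

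At 252 per arm the conclusion is conditional: 75.6% at 26.6%, 80.2% at 26%. Even in the worse case, the test's conservatism explains only about 3 of the 4.4 points.

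The power figures assume a two-sided test, a true placebo rate of 38%, and one of these two treatment rates. The 26.6% comes from reading the 30% as relative; the 26% is inferred from the printed 252.

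**What to change.** 1. In 10.1, state the treatment-arm rate, whether the 30% is relative or absolute, the sidedness, and the test or formula behind 252.
2. In 10.1, restate the power for Fisher's test at the 240 per arm expected after attrition: about 73% if the rate is 26.6%, about 78% if it is 26%.
3. Reconcile 600, 504 and 20%. Either enrol 630, or keep 600 and report the power at 480 completers, or justify an attrition rate of 16%.
4. Optionally, name Boschloo's exact test for the STS comparison in 10.2. It keeps the 5% level and at 240 per arm gives 75.9% for 26.6% and 80.3% for 26%, a gain of about 2 points without more subjects. It should be chosen before unblinding.

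Items 1, 2 and 4 cost only wording and a less favourable stated power. Item 3 costs 30 more enrolments if 504 completers are to be kept. If 26.6% was intended and 80% with Fisher is still required, the cost is 98 more (698 − 600). Whether to pay that is the sponsor's decision.

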1.2 Secondary Objective

1.2.1 To determine whether administering oral D-methionine can prevent tinnitus after required M-16 weapons training. This aim will be addressed by comparing the results of D-methionine versus placebo administration starting 3 days prior to, during the 11 day period of weapons training (over a 2 week period), and 4 days after weapons training for a total of 18 days of dosing. Tinnitus questionnaires will be completed before weapons training and 11-15 days after the last day of study drug/placebo administration.

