4.2.2 Secondary Endpoint

- Secondary efficacy endpoint is change from baseline in scores for the tinnitus scales for both loudness and annoyance.

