Subjects will be administered the tinnitus questionnaires at the time of their initial and final audiometric evaluations. Differences in the questionnaire scores will be compared pre- and post-noise in the same subject and between treatment groups. In addition to the THI, an important measure for use in evaluating potential preventive or treatment effects for tinnitus is that of magnitude scaling for the subjective loudness dimension of tinnitus. Subjective ratings for tinnitus, using a scale from 0 – 10, are well documented by a number of investigators (Meikle, 1992; Levine, 1999; Bauman and Jastreboff, 1999; Newman et al., 1996). Such ratings are quickly and easily administered, and can be efficient measures for quantifying tinnitus treatment effects. The subjective loudness rating for tinnitus captures the aversive aspect of tinnitus, in a similar manner to that of pain rating scales, which are widely used by pain experts to quantify the aversive aspect of chronic pain. It has the advantage that it does not require the subject to try and recall his or her tinnitus problems during a preceding time interval (such as a week or more), but instead can be given as an immediate and current rating of the tinnitus magnitude.

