1. To determine if there is a significant difference in reported level of tinnitus between the D-methionine and the placebo groups where the level (loudness) of tinnitus will be scored on an eleven point scale with a value of 0 associated with very quiet and a value of 10 associated with very loud and on an eleven point scale where the degree of annoyance secondary to the tinnitus will also be scored on an eleven point scale with a value of zero indicating that it is not bothersome and a value of 10 indicating that it is unbearable. Repeated measures analysis of variance (ANOVA) will be utilized to determine significance.

The 95% confidence intervals will be estimated for all D-methionine vs. placebo differences.

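### The tinnitus analysis does not say which repeated measures ANOVA term is tested; baseline-adjusted ANCOVA would settle this and gain power at no cost

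*Combined protocol and SAP*

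**What the plan says.** Section 4.2.2 sets the endpoint: "Secondary efficacy endpoint is change from baseline in scores for the tinnitus scales for both loudness and annoyance". The Clinical Synopsis (main parameters of efficacy) agrees.

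Section 10.2 words the matching objective as "To determine if there is a significant difference in reported level of tinnitus between the D-methionine and the placebo groups". Each rating is on a 0 to 10 scale, and the method is one sentence: "Repeated measures analysis of variance (ANOVA) will be utilized to determine significance". Neither a model term nor the baseline score is mentioned. The Synopsis entry on statistical analysis also speaks of level. Section 10.2 closes by promising 95% confidence intervals for all arm differences.

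There are two measurements. Section 5.5.1: "Subjects will be administered the tinnitus questionnaires at the time of their initial and final audiometric evaluations". Section 1.2 gives the timing: "Tinnitus questionnaires will be completed before weapons training and 11-15 days after the last day of study drug/placebo administration". Section 6.3 places the final visit on Days 29-32.

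Section 5.5.1 also describes the comparison: "Differences in the questionnaire scores will be compared pre- and post-noise in the same subject and between treatment groups".

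**The concern.** A two-arm, two-visit repeated measures ANOVA yields three tests: group, visit, and group by visit. Only group by visit corresponds to change from baseline compared between arms. An analyst who follows the Section 10.2 wording literally, as a between-arm difference in level, could report the group term. An analyst who follows Sections 4.2.2 and 5.5.1 would report group by visit. The two can give different estimates and different p-values from the same data, and the plan does not fix the choice before the data are seen.

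The hearing-threshold item in the same section is more explicit. It refers to change, to interaction effects and to computation relative to baseline. The tinnitus item has none of these.

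A second issue remains whichever term is meant. A baseline rating is collected from every subject, and neither term uses it as efficiently as adjusting the final score for it.

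**Working it through.** **Inputs.** The documents give no SD, effect size, correlation or power for the tinnitus ratings, so there is no plan figure to reproduce.

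- From the documents: two visits; 252 completers per arm (Section 10.1, sized on significant threshold shift and not on tinnitus); α = 0.05. Sidedness is not stated; two-sided is used here.
- Assumed: SD of 1 at both visits; a true final-visit arm difference d of 0.25 SD; arms equal at baseline by randomisation; baseline-final correlation ρ of 0.3, 0.5 and 0.7. Section 5.5.1 quotes a test-retest r of .92, but for the Tinnitus Handicap Inventory, which is a different instrument.

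**What each test estimates.**

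1. Group main effect: compares subject means over the two visits. Expected difference (0 + d)/2 = d/2; per-subject variance (1+ρ)/2.
2. Group by visit: with two visits this is the t-test on change. Expected difference d; variance 2(1−ρ). In one simulated trial the interaction F and the squared t on change were both 9.0722.
3. ANCOVA of the final score on arm and baseline: expected difference d; variance 1−ρ².

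The halving in item 1 depends on neither the SD nor ρ. In 4,000 simulated trials at each of ρ = 0.5, 0.7 and 0.92, with a true difference of −0.25, the main effect averaged −0.126, −0.126 and −0.123. The change score averaged −0.247, −0.250 and −0.249.

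**Power.** z = effect / √(2 × variance / 252), compared with 1.96. At ρ = 0.5:

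- main effect: 0.125 / √(2 × 0.75 / 252) = 0.125 / 0.0772 = 1.62, power 37%
- change: 0.25 / √(2 × 1 / 252) = 0.25 / 0.0891 = 2.81, power 80%
- ANCOVA: 0.25 / √(2 × 0.75 / 252) = 0.25 / 0.0772 = 3.24, power 90%

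| ρ | Group main effect | Change (group by visit) | ANCOVA |
|---|---|---|---|
| 0 | 51% | 51% | 80% |
| 0.3 | 41% | 66% | 84% |
| 0.5 | 37% | 80% | 90% |
| 0.7 | 33% | 95% | 98% |
| 0.92 | 30% | >99% | >99% |

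**Ratios that do not depend on d.**

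- Signal of main effect to change: [(d/2)/√((1+ρ)/2)] / [d/√(2(1−ρ))] = √((1−ρ)/(1+ρ)). This is 1.00 at ρ = 0 and 0.58 at ρ = 0.5, so the main effect loses power to change whenever ρ is above 0.
- Efficiency of change relative to ANCOVA: (1−ρ²)/(2(1−ρ)) = (1+ρ)/2. This is 65%, 75% and 85% at ρ = 0.3, 0.5 and 0.7.

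**Unequal variances.** With SDs s₁ at baseline and s₂ at the final visit, the change-score variance minus the ANCOVA variance is (s₁² + s₂² − 2ρs₁s₂) − s₂²(1−ρ²) = (s₁ − ρs₂)². This is never negative, so in large samples ANCOVA is at least as efficient as change even when the visit variances differ.

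**The case against.** The strongest reply is that the plan never says the group main effect is the test. A reader might infer from the word level that it is, and conclude that the planned analysis halves the treatment effect and would probably miss a real benefit. The documents do not support that. In the Section 10.2 sentence, level is glossed as loudness and may simply name the rating. No ANOVA term is chosen. Sections 4.2.2 and 5.5.1 both point to change, and on that reading nothing is halved and the test matches the endpoint.

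The power loss under the main-effect reading also depends on the assumed effect. With d = 0.5 SD the main effect is 0.25, and z = 0.25/√((1+ρ)/252) = 3.48, 3.24 and 3.04 at ρ = 0.3, 0.5 and 0.7, giving power of about 94%, 90% and 86%. Halving the estimate does not halve the test statistic, because the standard error changes too; at ρ = 0 the main effect and change have equal power.

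It can also be said that a change-score test is valid in a randomised trial, so replacing it is a matter of efficiency and not of correction.

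All of this stands. It does not remove the ambiguity: the analysis section is where the test should be fixed, and there the term is missing. Nor does it answer the efficiency point, which applies even to the favourable reading.

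**Conclusion.** The finding is an unspecified test plus an available gain, not a demonstrated error. If the group term were used, the estimate would be half the final-visit effect, and the promised confidence interval would be centred on that half. If group by visit is used, the analysis matches the endpoint but has (1+ρ)/2 of the efficiency of ANCOVA under equal variances. For a 0.25 SD effect at 252 per arm, that costs 18, 10 and 3 percentage points of power (rounded) at ρ = 0.3, 0.5 and 0.7.

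The halving is exact given equal expected baselines. The power figures rest on the assumed effect, the assumed correlations and equal visit variances; equal variances are not assured for bounded ratings taken before and after noise exposure. The ordering of ANCOVA over change does not need equal variances.

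Under randomisation the baseline-adjusted difference in final score targets the same arm difference as change from baseline, so the endpoint in Section 4.2.2 is kept. This is a free improvement to a secondary analysis and does not touch the primary endpoints.

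**What to change.** In Section 10.2, for loudness and for annoyance separately, replace the repeated measures ANOVA with ANCOVA of the Day 29-32 score on treatment arm and baseline score, and report the adjusted arm difference with its 95% CI. Align the wording of the objective there and in the Synopsis with change from baseline.

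If the repeated measures ANOVA is kept, state at minimum that the group-by-visit (change) contrast is the test for each scale.

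The cost is one sentence of analysis text and the matching Synopsis line. Both scores are already collected, so there are no added visits, data or subject burden.
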